#### 5.14.4. Laboratory Analyses

All laboratory measurements including scheduled and unscheduled will be listed by patient by visit using all randomized patients. An additional listing will be presented for selected laboratory measurements that are outside the normal range. The normal ranges are defined by a lower limit of normal (LLN) and an upper limit of normal (ULN). A result that is greater than or equal to the LLN and less than or equal to the ULN is considered to be within the normal ranges.

Laboratory measurements will be summarized with respect to observed values and change from baseline by treatment group at each scheduled visit. For each analyte, the change from baseline to endpoint will be tested using Wilcoxon rank-sum test. Also, laboratory analytes with categorical responses will be summarized using frequency and percentage by visit and treatment group. Treatment comparisons will be performed using a Fisher's exact test.

The proportion of patients with treatment-emergent abnormal values defined by the outside of the normal ranges will also be summarized by treatment group and compared between treatment groups. The proportion will be calculated by dividing number of patients with abnormal value after baseline by number of patients with baseline and post-baseline values (patients who had abnormal baseline value in a same direction of interest will be excluded).

#### 5.14.4.1. Amylase and Lipase

For amylase and lipase, the following variables will be analysed:

- Number and percent of patients having measurements above ULN/2xULN/3xULN at screening (Visit 1), baseline (Visit 3), and each post-randomization visit (Non-cumulative and cumulative incidence)
- Number and percentage of patients having measurements above ULN at baseline (Visit 3) with post-randomization values decreased from baseline at each visit.
- Number and percentage of patients having measurements above ULN at baseline (Visit 3) with post-randomization values increased from baseline at each visit.
- 4) Number and percentage of patients having normal measures at baseline (Visit 3) with post-randomization values increased from baseline above ULN/2xULN/3xULN at each visit.

The cumulative number of patients having amylase above ULN at post-randomization visit is the number of patients having amylase above ULN at least once at any post-randomization visit (e.g. patients with repeatedly increased value are counted only once). The same holds for lipase.

#### 5.14.4.2. Calcitonin

Threshold analyses will be performed for calcitonin. Some of these analyses involve a composite criterion involving change from baseline of at least 50%. For alignment with the calcitonin monitoring algorithm used in study, the baseline value for this analysis will be the mean of all nonmissing baseline observations. In cases where baseline is missing but postbaseline is available, the percent-change criterion will be assumed to be satisfied. Following threshold analyses will be provided:

- postbaseline calcitonin  $\geq 20$  pg/mL
- postbaseline calcitonin  $\geq$  35 pg/mL

Additionally, for each of these, a threshold analysis will be presented of patients also satisfying a change from baseline of  $\geq$ 50%.

A shift table will be provided of postbaseline calcitonin to and from the following categories: (i) <20 pg/mL, (ii)  $\geq 20 \text{ pg/mL}$  and <35 pg/mL, (iii)  $\geq 35 \text{ pg/mL}$ .

#### 5.14.4.3. Lipid

Actual value and percent change from baseline at each visit for lipid measurement will be summarized by treatment group using safety analysis set. For the percent change from baseline to Visit 7, wilcoxon rank-sum test will be conducted.

The lipid measurements to summarize in this study are "Cholesterol (milligram/deciliter)", "Direct LDL Cholesterol (milligram/deciliter)", "HDL Cholesterol (milligram/deciliter)", "Triglycerides (milligram/deciliter)". LDL cholesterol is also calculated using the Friedwald equation. In addition, LDL cholesterol is calculated using the Friedwald equation only for the patients with TG (Triglyceride) < 400mg/dL. For the patients does not have a direct LDL

cholesterol, but LDL cholesterol can be calculated with Friedwald equation, then the LDL cholesterol value based on the Friedwald equation will be included for this summary.

#### 5.14.5. Physical Characteristics and Vital Signs

The vital signs include measurements of blood pressures, body weight and BMI.

Each patient will have their pulse rate and blood pressure measured 3 times. The measurements will be averaged separately for each patient at each visit; the average values will be used in the descriptive summaries and analyses.

Descriptive statistics for the actual measurements and change from baseline by visit and treatment group will be presented. For the change from baseline to Visit 7, wilcoxon rank-sum test will be conducted.

The incidence of patients with at least 1 measurement above the following levels after baseline will be summarized by frequency and percentage for each treatment group (Table GBGF 5.3). At the Visit 7, treatment comparisons between treatment groups will be performed using Fisher's exact test.

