## 5. A Priori Statistical Methods

## 5.1. Determination of Sample Size

A total of approximately 160 patients (dulaglutide: 120 patients; placebo: 40 patients) will be randomized to have approximately 136 completers (dulaglutide : 102 patients; placebo: 34 patients) to show dulaglutide is superior to placebo with more than 99% power assuming a treatment difference of 1.0% in HbA1c reduction, standard deviation (SD) = 1.0%, and dropout rate of 15%. The screen failure rate is estimated as 20%. Approximately 200 patients will be screened.

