#### 5.2. General Considerations

Statistical analysis of this study will be the responsibility of Lilly or its designee. Any change to the data analysis methods described in the protocol will require an amendment ONLY if it changes a principal feature of the protocol. Any other change to the data analysis methods described in the protocol, and the justification for making the change, will be described in the clinical study report (CSR). Additional exploratory analyses of the data will be conducted as deemed appropriate.

All analyses will be implemented using Version 9.1.3 SAS or higher.

Continuous data will be summarized in terms of the number of observations (n), mean, standard deviation (SD) and/or standard error of the mean (SEM), median, minimum (Min), and maximum (Max).

Categorical data will be summarized in terms of the number of observations (n), frequency count, and percentages. Percentages will be rounded to one decimal place. Percentages will not be presented for zero counts. Unless noted otherwise, percentages will be calculated using n (the number of observations with non-missing values) as denominator.

For efficacy analysis based on mixed-model for repeated measures (MMRM), summary statistics will be provided for the observed value and change from baseline value for each arm based on MMRM. Also, for efficacy analysis, statistical tests (including MMRM and ANCOVA) will only be conducted during the double-blind primary treatment period at each visit (i.e. Visit 4, 5, 6 and 7) and will not be conducted for time point after Visit 7.

For safety analysis, summary statistics will be provided for each arm during the both doubleblind primary treatment period (i.e. Visit 3 to 7) and entire study period (i.e. Visit 3 to 13). Table GBGF 5.1 gives the treatment groups to be displayed for each treatment period.

Unless otherwise specified, all tests of treatment effects will be conducted at a 2-sided alpha level of 0.05, and confidence intervals (CIs) will be calculated at 95%, 2-sided. All tests of interactions between treatment groups and other factors will be conducted at a 2-sided alpha level of 0.10. There will be no multiplicity adjustment for pairwise treatment comparisons.

List of analysis (LOA) will contain the list of all tables, figures and listings (TFLs), and will be provided separately.

			Between-Group Comparison When
Treatment Period	Treatment Groups	Abbreviation	Applicable
Double-blind	Placebo	Plc	Dula vs Plc

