#### 5.10.2.4. Analysis of Body Weight

Analysis of body weight based on MMRM will be summarized by treatment group using FAS.

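### Pulse rate and blood pressure, as continuous measures, are compared between arms only by a Wilcoxon test on change, with no baseline covariate and no between-arm difference or confidence interval

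*SAP*

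**What the plan says.** - **Vital signs (SAP 5.14.5).** Three readings are averaged per patient and visit. Descriptive statistics of value and change are given by visit and arm, and then: "For the change from baseline to Visit 7, wilcoxon rank-sum test will be conducted". No covariate, between-arm estimate or interval is named. Exceedances of fixed limits for systolic pressure, diastolic pressure and pulse are compared with Fisher's exact test.
- **Laboratory analytes (SAP 5.14.4).** For each analyte, "the change from baseline to endpoint will be tested using Wilcoxon rank-sum test".
- **Lipids (SAP 5.14.4.3).** "For the percent change from baseline to Visit 7, wilcoxon rank-sum test will be conducted".
- **Body weight.** SAP 5.14.5 states: "The vital signs include measurements of blood pressures, body weight and BMI". Weight therefore falls under the Wilcoxon test. It also has its efficacy analysis in SAP 5.10.2.4: "Analysis of body weight based on MMRM will be summarized by treatment group using FAS". That model carries the baseline value, the HbA1c stratum and the insulin regimen (SAP 5.10.2).
- **General rules.** Under SAP 5.2, "all tests of treatment effects will be conducted at a 2-sided alpha level of 0.05". Protocol 10.3.1 says that comparisons of continuous measures will be shown as differences in least-squares means with 95% intervals. SAP 5.14 and Protocol 10.3.4 say that safety p-values serve as guidance only.
- **Data available.** The Schedule of Activities has vital signs at Visits 3, 4, 5, 6 and 7.

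**The concern.** Comparing safety between the arms over 16 weeks is a secondary objective, and Protocol 10.3.4.5.2 places pulse rate and blood pressure under cardiovascular safety. A comparison of that kind is most useful as an estimated difference with an interval, particularly when p-values are only guidance and the placebo arm has 34 to 40 patients. A rank test on change supplies a p-value alone.

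The test also leaves precision unused. Subtracting baseline removes the baseline level but adds the baseline measurement's noise. Using baseline as a covariate removes only as much as the correlation supports. The continuous secondary efficacy measures in SAP 5.10.2 are adjusted this way; pulse and blood pressure are not.

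Finally, a patient with no Visit 7 value contributes nothing to the Visit 7 test, and SAP 5.14.5 states no handling for that. Patients who stop treatment leave the study (Protocol 8.2). A repeated-measures model would use their readings from Visits 4 to 6.

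**Working it through.** **Inputs from the documents.** Two-sided alpha 0.05 (SAP 5.2); 120 and 40 randomised, 102 and 34 completers (SAP 5.1).

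**Assumed inputs, not in the documents.** Baseline-to-Week-16 correlation r from 0.5 to 0.8; true difference 0.4 SD (for example 4 beats/min if the pulse SD were 10); equal SD at both times; normal data unless stated.

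**1. The plan's own figure.** SAP 5.1 sizes the trial "to show dulaglutide is superior to placebo with more than 99% power assuming a treatment difference of 1.0% in HbA1c reduction", with SD 1.0%.
- SE = 1.0 × √(1/34 + 1/102) = 0.198.
- 1.0/0.198 = 5.05, and Φ(5.05 − 1.96) = 99.9%. The noncentral t gives the same.
- 136/0.85 = 160.

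The figure reproduces. It concerns HbA1c only; no power or detectable difference is stated for vital signs or laboratory values.

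**2. Formulas, in units of the cross-sectional SD.**
- SD of change: √(2(1 − r)).
- For the Wilcoxon test, multiply by √(π/3) = 1.023, because its efficiency is 3/π under normality.
- Residual SD for analysis of covariance (ANCOVA): √(1 − r²).
- Power = Φ(0.4/(SD × 0.198) − 1.96).
- Variance ratio, ANCOVA to Wilcoxon: (1 + r)/2 × 3/π, which is 0.75 × 0.955 = 0.72 at r = 0.5 and 0.90 × 0.955 = 0.86 at r = 0.8.

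At r = 0.5, Wilcoxon: 0.4/(1.023 × 0.198) = 1.97, power 51%. ANCOVA: 0.4/(0.866 × 0.198) = 2.33, power 65%.

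**3. Results, 102 v 34.**

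| r | Wilcoxon power | ANCOVA power | Loss (points) | Detectable at 80% power: Wilcoxon | ANCOVA |
|---|---|---|---|---|---|
| 0.5 | 50.6% | 64.5% | 13.9 | 0.57 SD | 0.48 SD |
| 0.6 | 59.7% | 71.4% | 11.7 | 0.51 SD | 0.44 SD |
| 0.7 | 72.2% | 80.7% | 8.5 | 0.44 SD | 0.40 SD |
| 0.8 | 87.7% | 92.0% | 4.3 | 0.36 SD | 0.33 SD |

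With all 120 v 40, power is 57%, 67%, 79% and 92% (Wilcoxon) against 72%, 78%, 87% and 96% (ANCOVA).

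The loss also depends on the assumed difference. At 0.2 SD it is about 5 points throughout (16.5% v 21.4% at r = 0.5; 34.5% v 39.1% at r = 0.8).

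**4. Simulation check** (4,000 runs per setting, 102 v 34). Wilcoxon v ANCOVA: 48% v 62%, 58% v 69%, 72% v 80% and 86% v 91%. With no true difference (2,000 runs) the rejection rates lay between 4.3% and 5.8% for both methods, so both are valid.

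**5. Skewed data.** With lognormal errors the order reverses: Wilcoxon 77% v raw-scale ANCOVA 71% at r = 0.5, and 97% v 83% at r = 0.7. The power argument therefore does not carry over to skewed analytes.

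**6. What an interval would add.** The half-width of the adjusted 95% interval is about 1.96 × 0.198 × √(1 − r²): 0.34 SD at r = 0.5 and 0.23 SD at r = 0.8. With an assumed pulse SD of 10 that is 3.4 and 2.3 beats/min, a direct statement of what the trial can exclude.

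**The case against.** The strongest reply is that little depends on this test. Safety p-values are guidance, the sample size was set for HbA1c, and safety is also judged from changes by visit, threshold and shift analyses, treatment-emergent abnormal values and adjudicated events. The test holds its error rate. That stands, and it limits the point to efficiency and reporting.

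It can also be argued that the Protocol 10.3.1 sentence presupposes a fitted model and so does not reach a rank test. The sentence is not limited to efficacy. Even on the narrower reading, the SAP still offers no between-arm estimate for these measures.

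A reader might infer more than the documents support:
- **That baseline is ignored.** Change is follow-up minus baseline (SAP 5.2.2); only the covariate is missing. Lipids use percent change.
- **That no effect size is reported.** Mean changes per arm are tabulated, so a crude difference can be derived. What is absent is a planned between-arm difference with an interval.
- **That a safety signal will be missed.** This would require safety to be decided on Wilcoxon significance, which the plan disclaims.
- **That laboratory tests lose power.** Step 5 shows that the rank test can be the stronger one.
- **That body weight has two rival analyses.** Weight is a secondary efficacy endpoint analysed by the adjusted model; the test in 5.14.5 is only redundant.
- **That the laboratory endpoint is undefined.** Protocol 10.3.1 and Table GBGF 5.1 confine comparisons to the double-blind period. After baseline, hematology and chemistry are scheduled in that period only at Week 16 or early termination. Only the use of early-termination values remains open.

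**Conclusion.** The point holds for pulse rate and for systolic and diastolic pressure. Their only between-arm comparison as continuous measures is an unadjusted Wilcoxon test on change to Visit 7, with no planned difference or interval, and this does not carry through the general rule in Protocol 10.3.1. For roughly normal data at 102 v 34 it gives up about 4 to 14 points of power at a difference of 0.4 SD, or 14% to 28% of the information. Those figures rest on the assumed correlation of 0.8 to 0.5, the assumed difference and equal variances; none comes from the documents. The comparator is ANCOVA at a single visit, and any further gain from a repeated-measures model is not quantified. For laboratory analytes and lipids the point is limited to the missing estimate and interval. This is an inexpensive improvement to a valid, guidance-only analysis; no primary conclusion is affected.

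**What to change.** - **SAP 5.14.5.** Analyse systolic pressure, diastolic pressure and pulse rate with the repeated-measures model used for body weight: baseline value, HbA1c stratum, insulin regimen, treatment, visit and treatment-by-visit. Write out the visit terms, because SAP 5.10.2 does not list them for secondary measures (the Protocol synopsis does). Report the Week 16 least-squares mean difference with its 95% interval. Keep the Wilcoxon test as supportive.
- **SAP 5.14.4 and 5.14.4.3.** Keep the rank test, or use log-scale ANCOVA for skewed analytes. Add a between-arm estimate with a 95% interval: Hodges-Lehmann with the rank test, or a back-transformed ratio with the log-scale model. State whether early-termination values count as the endpoint.
- **Body weight.** Drop it from the Wilcoxon test in 5.14.5; the analysis in 5.10.2.4 covers it.

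The cost is SAP wording and re-use of a model that is already planned. No new data are needed.

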#### 5.14. Safety Analyses

Unless otherwise specified, the safety analysis set will be used for analyses of safety measurements. Also, p-values provided from all safety analyses will be used for guidance purposes only.

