#### Table GBGF 5.3. Vitals Threshold for Study H9X-JE-GBGF

Systolic Blood Pressure (mm Hg)	-
≥140	
Diastolic Blood Pressure (mm Hg)	
≥90	
Pulse Rate (beats per minute)	
>100	

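### The vital-sign threshold table reports as incidence a count that includes patients already over the threshold at baseline, with no baseline-conditioned companion analysis

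*SAP*

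**What the plan says.** SAP 5.14.5 (Physical Characteristics and Vital Signs) states: "The incidence of patients with at least 1 measurement above the following levels after baseline will be summarized by frequency and percentage". The levels, in "Table GBGF 5.3. Vitals Threshold for Study H9X-JE-GBGF", are absolute: systolic ≥140 mm Hg, diastolic ≥90 mm Hg, pulse >100 per minute. There is no condition on the baseline value, no minimum change, no stated denominator and no shift table. For the comparison, "At the Visit 7, treatment comparisons between treatment groups will be performed using Fisher's exact test".

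The general rule in SAP 5.2 is that, unless noted otherwise, "percentages will be calculated using n (the number of observations with non-missing values) as denominator".

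In SAP 5.14.4, by contrast, the treatment-emergent laboratory proportions need both a baseline and a post-baseline value, and "patients who had abnormal baseline value in a same direction of interest will be excluded".

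Two other statements bear on the weight of the point. SAP 5.14.5 also plans descriptive change from baseline by visit, and "For the change from baseline to Visit 7, wilcoxon rank-sum test will be conducted". SAP 5.14 says that "p-values provided from all safety analyses will be used for guidance purposes only".

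**The concern.** Incidence normally means new occurrence. Under the text of 5.14.5, a patient with a systolic pressure of 150 at Visit 3 and 150 at Week 16 is counted in the same way as one who moved from 120 to 150. The table therefore mixes persistence with new onset under a label that suggests only the second.

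Protocol 6.1 and 6.2 contain no blood-pressure or pulse limit, so patients over a threshold can be randomized. How many there will be is not stated.

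Two things are at stake. A reader of the report cannot tell how many patients newly crossed a threshold on dulaglutide. And where persistence is similar in the two arms, the between-arm contrast is pulled towards no difference.

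**Working it through.** **1. The plan's own figure.** The SAP gives no figure for the vital-sign thresholds. Its only computable design figure is the primary power. With 102 v 34 completers, a difference of 1.0 and an SD of 1.0, the standard error is √(1/102 + 1/34) = 0.198, and 1/0.198 − 1.96 = 3.09, so power is 99.9%. This agrees with the stated figure of more than 99%, but does not bear on this point.

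**2. How the SAP's threshold analyses treat baseline.**

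| SAP section | All-patient threshold count | Analysis that uses baseline status |
|---|---|---|
| 5.14.4 Laboratory | – | Baseline-abnormal patients excluded |
| 5.14.4.1 Amylase, lipase | Yes | Row limited to patients normal at baseline |
| 5.14.4.2 Calcitonin | Yes | Added ≥50% change criterion; shift table |
| 5.14.7 eGFR, UACR | Yes | Shift tables |
| 5.14.5 Vital signs | Yes | None for the thresholds |

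That baseline-high patients are included is inferred from the silence of 5.14.5 together with the default denominator in 5.2. The SAP does not say so outright, but no other section supplies a baseline rule.

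**3. Effect on the contrast.** Let b be the proportion over the threshold at baseline (equal in expectation by randomization), p₁ and p₀ the new-onset proportions on dulaglutide and placebo among the rest, and q₁ and q₀ the proportions of baseline-high patients with a later high value.

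- All-patient proportion in arm i: Pᵢ = b·qᵢ + (1 − b)·pᵢ
- Risk difference: P₁ − P₀ = b·(q₁ − q₀) + (1 − b)·(p₁ − p₀)
- With q₁ = q₀ this becomes (1 − b)·(p₁ − p₀)

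**4. Numbers.** The arm sizes come from SAP 5.1: "A total of approximately 160 patients (dulaglutide: 120 patients; placebo: 40 patients) will be" randomized. Alpha is 0.05 two-sided (SAP 5.2). The documents give no b, p or q, so all are assumed. Power is exact for Fisher's test, by enumeration, at 120 v 40 for all patients and at 120(1 − b) v 40(1 − b), rounded, for the baseline-normal subset. The comparison is read as covering any value up to Visit 7.

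*Equal persistence of 80%, new onset 30% v 10%.* Without the baseline-high patients, the risk difference is 20 points and the risk ratio 3.0 throughout.

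| b | All patients: proportions | Risk difference (points) | Risk ratio | Power, all | Power, baseline-normal (n) |
|---|---|---|---|---|---|
| 10% | 35% v 17% | 18 | 2.06 | 57% | 69% (108 v 36) |
| 20% | 40% v 24% | 16 | 1.67 | 42% | 63% (96 v 32) |
| 30% | 45% v 31% | 14 | 1.45 | 33% | 57% (84 v 28) |
| 40% | 50% v 38% | 12 | 1.32 | 25% | 47% (72 v 24) |

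Example at b = 20%: 0.2 × 0.8 + 0.8 × 0.3 = 0.40, and 0.2 × 0.8 + 0.8 × 0.1 = 0.24.

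*Larger or smaller effect, equal persistence of 90%.* Power, all patients v baseline-normal subset:

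| New onset | b = 20% | b = 30% | b = 40% |
|---|---|---|---|
| 35% v 10% | 61% v 82% | 48% v 76% | 35% v 68% |
| 20% v 10% | 13% v 19% | 11% v 16% | 9% v 13% |

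*Few patients over the threshold at baseline (pulse-like), new onset 10% v 2%, persistence 80%.*

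- b = 2%: risk difference 7.8 v 8.0 points, risk ratio 3.2 v 5.0, power 25% v 27%.
- b = 5%: risk difference 7.6 v 8.0 points, risk ratio 2.3 v 5.0, power 20% v 24%.

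*Unequal persistence, new onset 35% v 10%.* Power, all patients v baseline-normal subset:

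| Persistence (dulaglutide v placebo) | b = 20% | b = 30% | b = 40% |
|---|---|---|---|
| 90% v 70% | 78% v 82% | 74% v 76% | 70% v 68% |
| 90% v 60% | 85% v 82% | 85% v 76% | 84% v 68% |

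In the second row the all-patient count is the more sensitive analysis at every prevalence shown.

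**The case against.** The strongest reply has four parts.

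*The baseline exclusion is not a uniform SAP rule.* It belongs to one laboratory analysis that is expressly treatment-emergent. Calcitonin, eGFR/UACR and amylase/lipase also have all-patient threshold counts, and 5.14.5 never uses the term treatment-emergent. This stands: counting all patients is a recurring convention here. What sets vital signs apart is that the companion analysis is missing.

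*Dilution depends on an assumption.* A reader might infer that including baseline-high patients weakens any blood-pressure or pulse signal because they add the same count to each arm. The documents do not support that. At 3:1 allocation the counts differ, and at best the expected proportions match. Even that needs the drug to have no effect on persistence. If it does have one, the loss can disappear or reverse, as the last table shows. Excluding those patients also discards data on people in whom a further rise may matter.

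*Other analyses remain.* The change-from-baseline summaries and the Wilcoxon test use each patient's own baseline and are untouched. This stands, but a shift in level does not show how many patients newly crossed a threshold.

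*Power is a weak yardstick.* Safety p-values are for guidance, the protocol asks only that pulse and blood pressure be summarized, and with a modest effect (20% v 10%) neither analysis has useful power. This also stands. It limits the weight of the point, but guidance-only p-values do not correct the label on the percentage.

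**Conclusion.** The gap is real and minor. As written, 5.14.5 counts patients already over a threshold as incident, and vital signs are the only threshold analysis compared above without an exclusion, companion row or shift table that uses baseline status.

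Under equal persistence the risk difference shrinks by (1 − b): from 20 points to 16 at 20% baseline prevalence and to 12 at 40%, in the 30% v 10% scenario. This matters mainly for blood pressure, where baseline prevalence could be substantial. For pulse above 100, at 2% prevalence, the risk difference loses 0.2 points and power about 2 points, although the risk ratio still falls from 5.0 to 3.2. All prevalences, persistence rates and onset rates are assumptions, and the direction of the effect depends on persistence being similar in the two arms.

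It would be too strong to infer that the trial cannot show a blood-pressure or pulse effect, or that the Fisher comparison is invalid. The test is valid for the all-patient proportion, the change-from-baseline analysis is unaffected, and the primary endpoint is not involved.

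**What to change.** In SAP 5.14.5, add a treatment-emergent row for each criterion in Table GBGF 5.3:

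- **Numerator:** patients who do not meet the criterion at baseline and meet it at least once afterwards.
- **Denominator:** patients who do not meet it at baseline and have a post-baseline value.
- **Baseline status by criterion:** systolic below 140, diastolic below 90, pulse at or below 100. The wording must respect the different inequality signs.
- **Comparison:** Fisher's exact test, as already planned.

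Keep the all-patient count beside it, relabelled as any post-baseline value meeting the criterion. It remains informative if persistence differs between arms.

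The cost is a change of SAP wording and one extra table row per criterion, with smaller denominators in that row (for example, 96 v 32 at 20% baseline prevalence). No new data are needed, because the protocol's Schedule of Activities already collects vital signs at Visit 3 and at each later visit.
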